more frequently), which will *not* be conducted in this study. We will be using a MagPro X100 device (MagVenture). This device has FDA 510(k) clearance (approval #K091940) for peripheral nerve stimulation, and has been cleared as a non-significant risk device by this and numerous other IRBs for research and clinical use. The most serious risk of TMS is induction of seizures. TMS-induced seizures are usually focal, but in some cases can become generalized. To minimize this risk, participants with underlying brain injury that increases the risk of TMS-induced seizures will be excluded from participation – this includes moderate or severe traumatic brain injury, stroke, tumor, multiple sclerosis, or abscess (see full list under Exclusion Criteria). Additionally, participants taking medications that significantly lower seizure thresholds, such as anti-psychotics, amphetamines, tricyclic antidepressants, bupropion, and dalfampridine will be excluded. Furthermore, the applied stimulus intensity will be kept below 200% of the motor threshold for each muscle. This intensity and single-pulse frequency fall far below the recommended safe guidelines delineated by an international workshop on TMS safety (Rossi et al. 2009). Furthermore, participants with implanted devices with electromagnetic properties, such as spine stimulators, deep brain stimulators, vagal nerve stimulators, cardiac pacemakers, cochlear implants, or aneurysm clips, will be excluded. The investigator who will be performing the TMS protocol ([name]) is a neurologist experienced in treating seizures. There is no risk of seizure from electrical stimulation below the brain, as performed in this protocol.

There is a theoretical risk of *repetitive* TMS causing acute psychotic or manic symptoms in patients with depression. This risk is not clearly above the risk for sham-TMS, and it is not clearly above the natural rate of psychotic or manic symptoms that may arise in subjects with depression. Regardless, this protocol does *not* meet the definition of repetitive TMS, and any subject with history of bipolar disease, active psychotic symptoms, or history of suicide attempt will be excluded.

TMS pulses generate loud auditory clicks. Hence, all participants will wear earplugs during the procedure. TMS may also cause scalp tingling sensations or pain that is almost always mild and transient. This occurs approximately half as frequently in participants exposed to sham-stimulation. This is much less common using single-pulse TMS than repetitive TMS. Our protocol will use only single-pulse TMS.

The research team has delivered TMS pulses at 5 to 10-second intervals extensively in prior and ongoing IRB-approved clinical studies. A standardized form to assess TMS side effects is used at the end of each TMS session. To repeat, the use of only single pulse TMS, as well as all the other precautions and exclusion criteria we will follow in our TMS protocol, far exceed the recommended guidelines established by an international group of TMS experts⁷¹.

The Brainsight optical TMS tracking system (Rogue Research) uses passive reflectors placed on the subject's head and the TMS magnet to track the magnet's position and orientation relative to the subject's brain in real time. This is a passive detection device, with no penetrating electromagnetic stimulation. The infrared optical tracking portion of the system meets all applicable conformity standards (ANSI/AAMI ES60601-1:2005 +C1:2009 +A2:2010; see appendices). The infrared optical tracking portion of this system has been incorporated into numerous surgical tracking systems that have obtained FDA 510(k) approval in the setting of invasive brain and organ surgery. However, when used in combination with non-invasive TMS for research, it is not considered a medical device that requires FDA approval. There is no risk to the subject from using this tracking system.

Study coordinators and research assistants will be trained to conduct all procedures in a safe and effective manner that produces reproducible results. Study personnel with experience working with SCI participants will supervise all sessions. All staff will have undergone the appropriate training to use the equipment properly and safely. All subjects will be thoroughly questioned after each procedure to ensure that all possible adverse events, expected and unexpected, are ascertained. Study personnel will refer participants to the proper medical or psychological resources for any identified conditions or problems as a consequence of the research.

In the event of a serious adverse event, it will be reported to the IRB within 24 hours and study interventions will be discontinued until the study physician states that it is safe to resume the study. Adverse events will

be recorded in a data sheet and reported annually to the IRB. When appropriate, necessary medical or professional intervention will be provided for any serious or regular adverse event warranting treatment.

Any unexpected complications that may occur will be discussed with the study physician and/or the participant's SCI physician. [name], a board-certified internist, will serve as the study physician.

Protection against Risk

Most of the information that participants provide will not be identifiable. Participant data results will be stored on the VA network in a password-protected file. No identifiable information will be linked to this file. The study team members will have a separate file of participant contact information, also stored on the VA network. Participants will be assured that any "hard copies" of their contact information or data will be kept in a securely locked cabinet in a locked private office. This data will not be destroyed. There is minimal risk of a breach of confidentiality or data security.

Study coordinators and research assistants will be trained to conduct all procedures in a safe and effective manner that produces reproducible results. Study personnel with experience working with SCI participants will supervise all sessions. All staff will have undergone the appropriate training to use the equipment properly and safely. All subjects will be thoroughly questioned after each procedure to ensure that all possible adverse events, expected and unexpected, are ascertained. Study personnel will refer participants to the proper medical or psychological resources for any identified conditions or problems as a consequence of the research.

In the event of a serious adverse event, it will be reported to the IRB within 24 hours and study interventions will be discontinued until the study physician states that it is safe to resume the study. Adverse events will be recorded in a data sheet and reported annually to the IRB. When appropriate, necessary medical or professional intervention will be provided for any serious or regular adverse event warranting treatment.

A formal Data Safety Monitoring Board will not be needed for this study.

Provisions for keeping data confidential are established. All electronic data will be kept on the secure VA network. All intake forms are de-identified according to HIPAA regulations. Consent forms, along with any other forms containing identifiable information, are kept in a locked filing cabinet. Only members of the investigative team will be able to use the information.

Any unexpected complications that may occur will be discussed with the study physician and/or the participant's SCI physician. [name], a board-certified internist, will serve as the study physician.

5. SIGNIFICANCE OF THIS RESEARCH.

The information obtained in this study may be useful scientifically to the subjects taking part in the study and to other researchers and patients. This could provide new information that leads to improved non-invasive techniques for strengthening nerve transmission after central nervous system injury.

Participants may achieve transient neurophysiological benefits. However, the study is not designed to provide long-lasting direct benefit. Rather, study participation may lead to new knowledge that could be applied toward the SCI population as a whole.

LIST OF KEY BIBLIOGRAPHIC REFERENCES.

1. Roy, F. D.; Bosgra, D.; Stein, R. B. Interaction of Transcutaneous Spinal Stimulation and Transcranial Magnetic Stimulation in Human Leg Muscles. *Experimental brain research* **2014**, 232, 1717–28.
2. Aimonetti, J. M.; Nielsen, J. B. Changes in Intracortical Excitability Induced by Stimulation of Wrist Afferents in Man. *The Journal of physiology* **2001**, 534, 891–902.

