Participants: Ages between 18 and 75. n=15 subjects with SCI. n=15 able-bodied volunteers.

Inclusion criteria

Able-bodied participants

1. Age between 18 and 75 years; n=15 for both Aims;
2. No known central or peripheral neurological disease or injury.

SCI participants

1. Age between 18 and 75 years; n=15 for Aims 1 and 2;
2. Chronic (> 12 months) motor-incomplete SCI between neurological levels {C1-C8};
3. Score of 2, 3, or 4 (out of 5) on manual muscle testing of wrist extension, wrist flexion, finger extension, finger flexion, or finger abduction in left or right hand;
4. Detectable F-wave responses of the left or right APB to median nerve stimulation and/or FDI to ulnar nerve stimulation;

Exclusion criteria

1. Multiple spinal cord lesions;
2. History of seizures;
3. Ventilator dependence or patent tracheostomy site;
4. Use of medications that significantly lower seizure threshold, such as tricyclic antidepressants, amphetamines, neuroleptics, dalfampridine, and bupropion;
5. History of stroke, brain tumor, brain abscess, or multiple sclerosis;
6. History of moderate or severe head trauma (loss of consciousness for greater than one hour or evidence of brain contusion or hemorrhage or depressed skull fracture on prior imaging);
7. History of implanted brain/spine/nerve stimulators, aneurysm clips, ferromagnetic metallic implants, or cardiac pacemaker/defibrillator;
8. Significant coronary artery or cardiac conduction disease;
9. Recent history (within past 6 months) of recurrent autonomic dysreflexia, defined as a syndrome of sudden rise in systolic pressure greater than 20 mm Hg or diastolic pressure greater than 10 mm Hg, without rise in heart rate, accompanied by symptoms such as headache, facial flushing, sweating, nasal congestion, and blurry vision (this will be closely monitored during all screening and testing procedures);
10. History of bipolar disorder;
11. History of suicide attempt;
12. Active psychosis;
13. Heavy alcohol consumption (greater than equivalent of 5 oz of liquor) within previous 48 hours;
14. Open skin lesions over the face, neck, shoulders, or arms;
15. Pregnancy
16. Unsuitable for study participation as determined by study physician.

Recruitment:

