Recruitment will be accomplished by pre-existing relationships, physician referrals, and IRB-approved advertisements. Veterans with SCI who have an ongoing relationship with personnel of the Center of Excellence for the Medical Consequences of SCI, such as those who attend the pulmonary, endocrine, cardiovascular, gastroenterology, and SCI clinics, will be informed about the study. Physicians at the James J. Peters VA Medical Center will be informed of the goals and aims and the inclusion/exclusion criteria for this study. Interested non-veterans who contact us through word of mouth, public online sites such as clinicaltrials.gov, or through participation in other ongoing studies at the Center of Excellence will also be informed about the study. We will not contact any patients unless referring physicians provide us with assurance that the patient would be interested in receiving further information about this study.

Eligibility Screening:

Persons interested in participating will be assigned a number beginning at 1. To determine eligibility, interested participants will be asked the “yes” or “no” questions listed below. Persons who answer “no” to any of the following questions will not be eligible for the study:

- Do you have a spinal cord injury, or are you an able-bodied volunteer?
- If you have spinal cord injury, did the injury occur greater than 12 months ago?
- Are you between the ages of 18 to 75 years?

If the potential participant answers “yes” to all questions, then the informed consent process will continue by inviting the participant for an in-person interview.

Enrollment:

At the in-person interview, the study will be explained by one of the study team members. All study team members will be trained to obtain consent. The study will be explained in its entirety. Along with explaining each of the testing and evaluation procedures, the study team member will explain every possible risk that the participant may encounter. The potential participant will be told that there is a possibility that he or she will not be eligible if any of the exclusion criteria are found to be true (i.e. a screening failure). This is an investigational, observational study. As such, no direct permanent benefits will be expected.

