- Interpretation: If subthreshold CES facilitation occurs at ISI between 2-20 ms, this would support the mechanism of heterosynaptic summation between segmental Ia input and descending corticospinal input¹. If facilitation occurs at ISI between 20-60 ms, this would support the mechanism of sensory cortical facilitation of motor cortex excitability (based on analogous findings using peripheral nerve stimulation^{4,2,3}). Because TMS travels along the same corticospinal and subcortical circuits used during volitional movement, this would also set the basis for using subthreshold CES to facilitate motor

responses during physical training programs (see Aim 2). Subjects with incomplete cervical SCI are expected to have reduced CES-TMS facilitation compared to uninjured subjects (see **Figure 4**).

CES-peripheral nerve interactions:

- Goal: Measure interactions between afferent and efferent cervical nerve roots, segmental interneuronal circuits, orthodromically conducting peripheral sensory fibers, and antidromically conducting peripheral motor fibers.
- Methods: F-wave pulse intensity will be ~110-120% of the intensity that results in maximal compound motor action potential (CMAP). H-reflex pulse intensity will be calibrated to result in H-reflex amplitude ~20-25% of maximal CMAP⁶³. Conditioning CES pulse intensity will be set between 30-175% of motor threshold, delivered within 300 ms of test pulses. For subthreshold conditioning CES, either single or “theta bursts” (3 pulses at 50 Hz)¹⁹ will be delivered. All pulse combinations will be delivered at a rate of 0.1 Hz, in pseudorandom parameter order, until 8 (CES-H combinations) or 25 (CES-F combinations) responses per parameter have been recorded.
- Hypothesis 1.2: Conditioning CES will increase persistence (number of responses per 25 stimuli) of median (APB) and ulnar (FDI) F-responses elicited up to 50 ms later.
- Hypothesis 1.3: Conditioning CES will reduce amplitude of median (FCR) H-responses elicited up to 50 ms later.
- Speculative hypothesis 1.2: Conditioning suprathreshold CES will block spinal motor neuron F-responses delivered up to 10 ms later.

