- Interpretation: These experiments will lead to multiple insights. Through segmental interactions, confirmation of Hypothesis 1.2 would further demonstrate the ability of CES to positively modulate motor neuron excitability, and confirmation of hypothesis 1.3 would indicate the potential for CES to reduce spasticity⁴⁵. Confirmation of speculative hypothesis 1.2 would demonstrate that at high intensity, CES pulses travel via efferent nerve roots and collide with retrogradely traveling F-waves.

Aim 1 data analysis: Peak-to-peak amplitude of all conditioned pulses will be normalized to the amplitude of unconditioned pulses. For each interaction paradigm, analysis of variance (ANOVA) with factors of subject group, stimulus intensity, interstimulus interval, and muscle will be performed. Post hoc pairwise comparisons will be made using Tukey’s method. *Power:* Using a conservative predicted effect size of 0.4 for each interaction paradigm, >80% power will be achieved with a sample size of 10 for each analysis (repeated measure ANOVA) with four factors. 15 subjects in each group (SCI, able-bodied) will undergo testing.

Aim 1 Timeline (Table 2):

Each subject will undergo three testing sessions on separate days, with a minimum of 24 hours and a maximum of two weeks between visits. Per subject, Aim 1 participation would therefore take 3 to 28 days. 30 subjects will be enrolled, resulting in 90 total testing sessions. A conservative projection of completing two testing sessions per week would result in a timeline of 45 weeks or 11-12 months for completing Aim 1.

Aim 2: Determine optimal CES parameters for acutely facilitating concurrent wrist and hand movements.

Volitional limb movements depend on the same corticospinal and spinal motor circuits as those activated by TMS and F-waves. Therefore, since preliminary data shows that subthreshold CES facilitates TMS responses, CES may also be able to facilitate volitional limb movements. The experiments in Aim 2 will shed light on this clinically applicable question.

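### The SCI versus able-bodied contrast is non-randomised and has no matching or adjustment for age or sex, so a systematic age or sex difference between the groups could be read as an injury effect

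*Combined protocol and SAP*

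**What the plan says.** All references are to the combined protocol and SAP, section 3.

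- **Participants and Inclusion criteria.** The sample is "n=15 subjects with SCI. n=15 able-bodied volunteers". The able-bodied criterion is "Age between 18 and 75 years; n=15 for both Aims" and the SCI criterion is "Age between 18 and 75 years; n=15 for Aims 1 and 2". The only further inclusion criterion for able-bodied volunteers is freedom from neurological disease or injury. Sex is not mentioned, apart from the exclusion of pregnancy.
- **Recruitment.** "Recruitment will be accomplished by pre-existing relationships, physician referrals, and IRB-approved advertisements". One named source is "Veterans with SCI who have an ongoing relationship with personnel of the Center of Excellence". Word of mouth, online listings and other studies at the centre are also allowed. No source is assigned to the able-bodied group, and no matching, stratification or quota by age or sex is described.
- **Enrollment.** "This is an investigational, observational study".
- **Aim 1 data analysis.** For each interaction paradigm, "analysis of variance (ANOVA) with factors of subject group, stimulus intensity, interstimulus interval, and muscle will be performed". The Aim 2 data analysis also includes subject group, with effort level, CES intensity, time bin and muscle. Neither model has an age or sex term.
- **CES-TMS interactions, Interpretation.** "Subjects with incomplete cervical SCI are expected to have reduced CES-TMS facilitation compared to uninjured subjects". This is the only directional statement about the group contrast.

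**The concern.** Group membership is injury status, so randomisation does not protect the comparison. If the two groups come from source populations that differ in age or sex, and either variable affects how strongly CES modulates a response, the subject-group term absorbs that effect. The same holds for the interactions of group with intensity, interval, time bin and muscle. A lower CES-TMS facilitation in the SCI group would agree with the stated prediction and would naturally be read as a consequence of injury. No analysis in the plan is prespecified to separate that reading from an age or sex difference.

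**Working it through.** **1. Which contrasts are exposed**

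| Contrast | Comparison | Open to age or sex confounding? |
|---|---|---|
| Hypotheses 1.1, 1.2, 1.3 | Conditioned vs unconditioned response, same person | No |
| Hypotheses 2.1, 2.2 | EMG after CES vs own baseline | No |
| Subject-group main effect, Aims 1 and 2 | SCI vs able-bodied | Yes |
| Group interactions, Aims 1 and 2 | Difference between groups in a within-person effect | Yes |

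**2. What the plan quantifies**

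The plan gives no figure for this contrast, so there is none to reproduce. Its power statements (effect size 0.4, sample size 10, power above 80%) do not address group imbalance. They do not state the effect-size metric, alpha or within-person correlation.

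**3. Illustration of a systematic age gap (all inputs assumed)**

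- Age SD if ages were spread evenly over 18-75: (75 − 18)/√12 = 57/3.46 = 16.5 years.
- Within-group age-outcome correlation r: 0.2 to 0.4.
- Systematic gap in mean age: 10 to 15 years.
- Shift in the group difference, in outcome SDs = r × gap / age SD.

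| Gap | r = 0.2 | r = 0.4 |
|---|---|---|
| 10 years | 0.2 × 10/16.5 = 0.12 | 0.4 × 10/16.5 = 0.24 |
| 15 years | 0.2 × 15/16.5 = 0.18 | 0.4 × 15/16.5 = 0.36 |

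With an age SD of 12 years the corners become 0.2 × 10/12 = 0.17 and 0.4 × 15/12 = 0.50. With r = 0 there is no shift. The direction could be either way.

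**4. Effect on the error rate of an unadjusted group test**

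This takes 15 vs 15, one summary value per person, two-sided 5% and no true group effect. The test statistic is a noncentral t with 28 df and noncentrality = shift × √(15/2).

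| Shift (SD) | False-positive rate |
|---|---|
| 0.10 | 5.8% |
| 0.15 | 6.8% |
| 0.20 | 8.3% |
| 0.30 | 12.5% |
| 0.40 | 18.5% |

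The 0.12-0.36 range therefore runs from about 6% to somewhere between 12.5% and 18.5%.

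**5. Can 15 per group carry an adjustment?**

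Assume a true group difference of 0.8 SD, which is what 0.4 would mean if it were Cohen's f for two equal groups. Adjust for age and sex, which costs 2 df. Noncentrality = 0.8 × √7.5 × √(1 − q)/√(1 − R²). Here R² is the outcome variance explained by the covariates (0 to 0.25), and q = D²/(D² + 4) for an age gap of D SDs.

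- Unadjusted: noncentrality 2.19, 28 df, power 56%.
- Adjusted, ages balanced (q = 0): power 56% (R² = 0) to 68% (R² = 0.25).
- Adjusted, mean ages 1 SD apart (q = 0.2): power 47% to 59%.

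Adjustment is feasible. Its main cost arises when the groups differ in age, which matching at recruitment prevents.

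**The case against.** The strongest reply is that this is a secondary contrast in a 30-person mechanistic study. Every numbered hypothesis is within-person. Aim 1 amplitudes are divided by each person's unconditioned response, Aim 2 EMG is divided by each person's baseline, and CES intensity is set relative to individual motor threshold. All of that is correct and it limits the weight of the point. It does not close it, because normalisation and threshold scaling remove differences in baseline size and excitability but not an age or sex effect on the degree of facilitation, which is the outcome.

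Several stronger readings are tempting, and the documents do not support them:

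- *That the SCI group will come mainly from clinics and the able-bodied group from elsewhere.* The Recruitment section gives no proportions, names clinic patients as one source, and does not limit the other routes to either group. A systematic age gap is possible but not shown.
- *That chance imbalance is itself bias.* If both groups came from the same even 18-75 distribution, the standard error of the mean age difference would be 16.5 × √(2/15) = 6.0 years, and a gap over 10 years would occur in about 10% of samples. That is sampling variation, already covered by the error rate of the group test.
- *That the shift is a given fraction of the planned effect.* The effect size of 0.4 has no stated metric. Reading it as Cohen's f for a group difference is an assumption, so the 0.8 SD above is not the protocol's benchmark.
- *That every group contrast has a directional prediction.* Only CES-TMS does.
- *That the investigators could never separate age from injury.* Nothing bars an exploratory adjusted analysis. The gap is that none is prespecified.

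**Conclusion.** The point holds for the SCI versus able-bodied contrast only, meaning the subject-group factor and its interactions in both ANOVAs. CES-TMS is where it matters most, because a group difference is predicted there. That contrast is non-randomised and has neither matching nor adjustment for age or sex. Hypotheses 1.1 to 2.2 stand as planned.

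The size of any bias cannot be derived from the documents. The shift of about 0.12-0.36 SD rests on an assumed systematic gap of 10-15 years, an assumed correlation of 0.2-0.4 and an assumed age SD of 16.5 years. No comparable figure is offered for sex. This is a worthwhile low-cost improvement and not a flaw in the study's main inferences.

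**What to change.** - **Recruitment.** Keep 15 per group. State that able-bodied volunteers will be frequency-matched to the accruing SCI group by broad age band and sex. Matching to the group as it accrues allows both groups to be enrolled in the same Aim 1 window, as Table 2 plans. Age is already checked at screening, so recording it in years, together with sex, adds no procedure.
- **Analysis.** Prespecify a sensitivity analysis of the group effect and group interactions that adds centred age, and sex if the groups are imbalanced on it. For the interactions, let the covariate interact with the same within-person factors, since an age main effect alone leaves them unadjusted. Report age and sex by group.
- **Interpretation.** State that the group contrast is observational, and read it alongside the adjusted result.

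**Cost.** Some able-bodied volunteers are deferred, so that group fills slightly later. The sensitivity model loses one or two between-person degrees of freedom. Sample size, visits and procedures do not change. Matching cannot be added once enrolment has closed, so it should be written in beforehand.
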